## 5.0 INTRODUCTION

### 5.1 Therapeutic Rationale

Ulcerative colitis (UC) is an inflammatory bowel disease (IBD) causing continuous mucosal inflammation of the colon without granulomas characterized by a relapsing and remitting course (Silverberg et al., 2005). Currently, the classification of IBDs is based on clinical parameters (activity, localization and phenotype). However, due to the high percentage of non-classifiable IBD (10%-15%) and the difficulty of a differential diagnosis, it has become necessary to search for new markers for these diseases (Díaz-Jiménez et al., 2011).

Ideally, a biomarker should be able to identify individuals at risk of developing the disease, detect the activity, monitor the effect of the treatment and, finally, have a prognostic value for the reactivation of the disease (Tibble and Bjarnason, 2001; Gisbert et al., 2007). Current biomarkers for IBD include serological levels of specific antibodies (ASCA, ANCA, anti-OmpC, anti-Cbir, antiglycans), serum C-reactive proteins (CRP) and cytokines and fecal proteins (calprotectin and lactoferrin). Nevertheless, the majority of these markers show a low sensitivity and/or specificity, and they cannot reflect the real intestinal damage (Díaz-Jiménez et al., 2011).

IL-33 is the newest identified member of the IL-1 family and exerts its biological effects through binding of its receptor, ST2 (human Suppression of Tumorigenicity 2). ST2 belongs to IL-1 receptor like 1 (IL-1RL1) super family, is coded by chromosome 2 and expressed mainly as 2 splice variants, namely transmembrane bound receptor, ST2L, that activates downstream signalling upon IL-33 recognition, and a serum soluble protein, sST2. Complex formation of IL-33 with sST2 leads to cytokine inactivation, suggesting a role for this variant form as a decoy receptor (Beltrán et al., 2010). The IL-33/ST2 axis is a intracellular signalling system that participates in processes as varied as the antigen/allergen response, autoimmunity, organ fibrosis and cardiac failure. Several studies reported an increase in plasma levels of sST2 in patients with inflammatory processes, including asthma, autoimmune, cardiovascular diseases, trauma and sepsis (Kuroiwa et al., 2001; Oshikawa et al., 2001; Weinberg et al., 2003; Brunner et al., 2004). Soluble ST2 protein was recently identified as a new and reliable biomarker of heart failure (Kohli et al., 2012).

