TNF inhibitors have improved outcomes of patients with moderate to severe ulcerative colitis, in spite some patients do not respond to treatment. Approximately one third of IBD patients are primary non-responders and fail to improve after therapy induction. In UC, mucosal healing is one of the most important clinical targets in order to maintain long-term remission. As mucosal healing has become a goal of treatment in IBD, endoscopy is the "gold standard" for the assessment of inflammation of intestinal mucosa. Surrogate markers that reflect the severity of mucosal inflammation and could potentially replace endoscopy are being investigated. Fecal calprotectin levels correlate significantly with endoscopic disease activity in IBD and is currently the best surrogate marker for the presence of intestinal inflammation. Still, the use of nonsteroidal anti-inflammatory drugs (NSAIDs), occurrence of intercurrent intestinal infection and the presence of malignancy may cause elevation of calprotectin levels in the absence of IBD.

A simple, rapid, sensitive, specific, inexpensive, non-invasive marker to detect and monitor intestinal inflammation is still needed. If such biomarker could also predict the clinical response to therapeutic regimens, its importance and impact for the patient would be greater.

Golimumab is a fully human anti-TNF $\alpha$  monoclonal antibody that binds with high affinity to human TNF $\alpha$  and inhibits TNF $\alpha$  bioactivity. A study recently conducted with 1228 patients (Sandborn et al., 2014a) has shown that golimumab induces clinical response in 51% of patients with moderate to severe UC at week 6, with remission and mucosal healing being achieved by 18% and 42% of patients, respectively. Among those patients on clinical response after induction with golimumab, 47-50% were able to maintain response through week 54 (50-100mg). At both week 30 and week 54, 23-28% of patients were in remission and 42-42% had mucosal healing (50-100mg). (Sandborn et al., 2014b)

No research so far correlated the levels of ST2 with endoscopic and histological activity in UC patients receiving anti-TNF- $\alpha$  therapy.

This is an exploratory study aiming to evaluate the potential of serum soluble ST2 as a surrogate biological marker of disease outcome and therapeutic response, in subjects with moderate to severe active UC who have an inadequate response to conventional therapies and who will start treatment with golimumab according to the SmPC.

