#### 7.7.2.2 Definition of Terms

- Moderate to severe active UC is defined in this study as a total Mayo score of 6 to 12, inclusive.
- The total Mayo Score, is a scale for assessing UC activity, it is the sum of 4 subscores and has values that range from 0 to 12. It includes assessment of Stool frequency (0-3) + Rectal bleeding (0-3) + Physician's global assessment (0-3) + Findings of endoscopy (0-3). Clinical remission: ≤2 points with no individual subscore > 1 ; Mildly active disease: 3-5 points; Moderately active disease: 6-10 points; Severely active disease: 11-12 points
- Endoscopic Mayo score (0-3): 0 = Normal or inactive disease, 1 = Mild disease (erythema, decreased vascular pattern, mild friability); 2 = Moderate disease (marked erythema, absent vascular pattern, friability, erosions); 3 = Severe disease (spontaneous bleeding, ulceration) - See Appendix 3.

- Partial Mayo score: Mayo score excluding the endoscopy subscore and has values that range from 0 to 9.
- Mucosal healing in this study will be determined by the endoscopy subscore of the Mayo score. Mucosal healing corresponds to endoscopy subscore of 0 or 1.
- Geboes index, is a validated score for evaluating histologic disease activity in UC as follows: grade 0, structural and architectural changes; grade 1, chronic inflammatory infiltrate; grade 2, lamina propria neutrophils and eosinophils; grade 3, neutrophils in the epithelium; grade 4, crypt destruction; grade 5, erosions or ulceration ; a higher score indicating more severe disease. Active histologic disease can be defined as a Geboes score  $\geq 3.1$  (presence of epithelial neutrophils with or without crypt destruction or erosions) (Geboes et al., 2000). - See Appendix 5
- Ulcerative Colitis Endoscopic Index of Severity (UCEIS) is a 3-item (vascular pattern, bleeding and erosion/ulceration) validated tool for assessing endoscopic severity of UC. Each item with three or four levels of severity, yielding a 9-point scale that accounts for 94% of the variance between observers in the overall assessment of severity (Travis et al., 2011) - See Appendix 4
- Clinical response is defined as a reduction in the Mayo score of at least 3 points and a decrease of at least 30% from the baseline score, accompanied by a decrease of at least 1 point in the rectal bleeding scale or an absolute rectal bleeding score of 0 or 1.
- Clinical remission is defined as Mayo score  $\leq 2$ , with no individual subscore exceeding 1.

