## 8.0 STATISTICAL AND ANALYTICAL PLAN

All quantitative variables will be summarize through descriptive statistics namely mean, median, standard deviation and range (minimum and maximum) and qualitative variables though absolute (n) and relative frequencies (%) and 95% confidence intervals (if applicable). The statistical analysis will be performed through frequency tables for qualitative variables and tables with descriptive statistics for quantitative variables.

The association between two quantitative variables will be performed through Pearson correlation coefficient or Spearman correlation coefficient, in case the normality assumption was not verified.

The association of two categorical variables will be tested through the Chi-Square test or Fisher Exact test (if applicable). Cohen's kappa coefficient will be performed.

The comparison of two independent samples in respect to quantitative variables will be performed through t-test for independent samples or the Mann-Whitney non-parametric test, according to the assumption validations of the statistical test.

ROC curve analysis will be performed as well as sensitivity, specificity, and positive and negative predictive values.

The primary analysis is to investigate the correlation between serum soluble ST2 and:

- endoscopic activity of disease (measured by Endoscopy Mayo subscore) at 6 weeks in UC subjects receiving golimumab, through the Spearman correlation coefficient;
- histological activity (measured by Geboes index score) at 6 weeks in UC subjects receiving golimumab, through the Spearman correlation coefficient.

Additionally, it will be obtained the cut-off of serum soluble ST2 levels at week 6 that optimizes sensitivity and specificity in the identification of disease activity through ROC curve analysis supplemented with analysis of sensitivity, specificity, and positive and negative predictive values. Endoscopic activity will be classified according to endoscopy subscore of Mayo score and histological activity will be classified according to Geboes index score.

For the analysis of the secondary endpoints the following analysis will be performed:

- the correlation between serum soluble ST2 with endoscopic activity of disease (measured by Endoscopy Mayo subscore) at 16 weeks in UC subjects receiving golimumab, through the Spearman correlation coefficient;

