Results for hematology (basophils, eosinophils, hematocrit, hemoglobin, lymphocytes, monocytes, neutrophils, platelets, RBC, WBC); blood chemistry (total bilirubin, ALT, AST, alkaline phosphatase, albumin, total protein, calcium, phosphate, sodium, potassium, chloride, urea and creatinine and CRP; urinalysis (proteins, glucose, nitrates, WBC, ketone bodies, hemoglobin, urobilinogen, bilirubin) will be summarized by total number of observations (n), mean, median, standard deviation, minimum and maximum.

Based on the recruitment capacity of sites it is expected to include a total of 37 subjects for analysis. With this sample size there is a probability of 80% that the lower limit of a one-sided 95% confidence interval is higher than 0.50, if the observed correlation coefficient is at least 0.75.

The primary analysis is to be performed on the Full Analysis Set, defined as all subjects who had received study medication and had at least one valid post baseline assessment for the primary endpoint that correlates ST2 with endoscopic activity.

In addition, a Per Protocol Set is defined as subjects receiving study medication, who meet key eligibility and evaluability criteria (without major protocol deviations). Sensitivity analyses will be based on this Per Protocol Set.

All safety analyses will be performed on the All Treated Set, comprising all subjects who received at least one dose of study medication.

No interim analysis is planned.

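### Sensitivity, specificity, PPV and NPV at the week-6 ST2 cut-off are estimated in the same 37 or so subjects used to select it, so they are biased upward on average

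*Combined protocol and SAP*

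**What the plan says.** Section 8.0 makes two week-6 Spearman correlations the primary analysis. As an addition it derives "the cut-off of serum soluble ST2 levels at week 6 that optimizes sensitivity and specificity in the identification of disease activity", using "ROC curve analysis supplemented with analysis of sensitivity, specificity, and positive and negative predictive values". This is done once per reference standard: "Endoscopic activity will be classified according to endoscopy subscore of Mayo score and histological activity will be classified according to Geboes index score". Section 7.7.3.2 treats an endoscopic subscore of 2 or more as active, and section 7.7.2.2 offers a Geboes score of 3.1 or more for histology. On cohort size, section 8.0 says "it is expected to include a total of 37 subjects for analysis".

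The optimality criterion is not named. No hold-out sample, cross-validation, bootstrap or pre-specified ST2 threshold appears for this step. The published threshold of 74.87 pg/mL in section 5.1 is background only. The Per Protocol analysis re-uses the same subjects, so it is not a validation sample.

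Section 8.0 also plans two further ROC-derived cut-offs for maintenance of response from week 6 to week 16: one for week-6 ST2 and one for the week-6 golimumab level.

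**The concern.** A threshold picked because it gave the best sensitivity and specificity in these subjects partly fits their chance variation. Accuracy quoted at that threshold in the same subjects includes that chance gain, which would not recur in new patients. The effect is largest when a class is small, and here about 37 subjects are divided between two classes.

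These figures matter to the protocol's own argument. Section 5.1 says "A simple, rapid, sensitive, specific, inexpensive, non-invasive marker to detect and monitor intestinal inflammation is still needed" and objects that for current biomarkers "the majority of these markers show a low sensitivity and/or specificity". It also cites 83% sensitivity and 83% specificity for ST2 in an earlier study. Readers are likely to set this trial's figures beside those, and without a corrected value or a stated limitation they would overrate the marker.

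**Working it through.** **1. The plan's own figure.** The 37 is justified for the correlation. By Fisher's z, n = ((1.645 + 0.842) / (atanh 0.75 − atanh 0.50))² + 3 = (2.487 / 0.4236)² + 3, which is about 37.4. The probability at n = 37 is Φ(√34 × 0.4236 − 1.645) = 79.5%. The plan's 37 and 80% are reproduced. No figure is given for the ROC step.

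**2. Inputs.**
- Cohort: 37 (section 8.0).
- Endoscopic split: section 5.1 cites another golimumab trial "with remission and mucosal healing being achieved by 18% and 42% of patients, respectively" at week 6, and section 7.7.2.2 says "Mucosal healing corresponds to endoscopy subscore of 0 or 1". So 37 × 0.42 = 15.5, taken as 16 inactive and 21 active. This is an assumption for the present trial.
- Histological split: not given. 30/7 is used as an unequal example.
- True AUC: 0.70 to 0.92. The upper value is cited in section 5.1; the range is assumed.
- Criterion: Youden (assumed, since none is named).
- Marker: N(0,1) in inactive and N(μ,1) in active subjects, with μ = √2 × Φ⁻¹(AUC).

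**3. Direction.** Let J be sensitivity + specificity − 1, c* the best cut-off in the population and ĉ the one selected. The apparent J at ĉ is at least the apparent J at c*, which averages J(c*). In turn, J(c*) is at least the true J(ĉ). So under the Youden rule the apparent J exceeds the true J of the selected cut-off on average. For the four separate figures the direction was checked by simulation.

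**4. Size at 21/16.** Mean apparent value vs mean true value at the selected cut-off, 2,500 simulated trials per AUC. True sensitivity is Φ(μ − ĉ) and true specificity Φ(ĉ); PPV and NPV use the sample class proportions.

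| True AUC | Sensitivity % | Specificity % | PPV % | NPV % |
|---|---|---|---|---|
| 0.70 | 70.0 vs 63.3 (+6.7) | 71.7 vs 62.4 (+9.3) | 78.8 vs 70.5 (+8.3) | 67.8 vs 58.6 (+9.2) |
| 0.80 | 77.5 vs 71.3 (+6.2) | 78.5 vs 70.3 (+8.2) | 84.0 vs 77.3 (+6.7) | 75.0 vs 67.0 (+8.0) |
| 0.92 | 88.0 vs 83.2 (+4.8) | 88.2 vs 81.7 (+6.5) | 91.4 vs 86.4 (+5.0) | 86.1 vs 80.1 (+6.0) |

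The apparent Youden index exceeded the true one in 87 to 93% of simulated trials. The mean apparent AUC was 0.70, 0.80 and 0.92, so it is unbiased.

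**5. Other assumptions.**
- At 30/7, specificity is overstated by about 12 to 17 points (Youden) or about 12 (closest to corner).
- At 21/16 with closest to corner, sensitivity and specificity are overstated by about 4 to 7 points.
- With an SD ratio of 1.2 (active to inactive), about 5 to 9 points. Section 5.1 suggests ln(367.90/90.65) / ln(65.32/20) = 1.40/1.18 = 1.18, if its ranges are quartiles.
- With the number active left random, AUC 0.60 to 0.92, 30%, 58% or 80% expected active, and other criteria and SD ratios, mean optimism was positive for all four figures in every scenario, from about 2 to 18 points.

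**6. What correction achieves.** Class-stratified bootstrap optimism correction, reselecting the cut-off in each resample, removed 62 to 67% of the bias at 21/16, 58 to 61% at 26/11 and 51 to 58% at 30/7. At 21/16 the reported values therefore fall by between 0.62 × 4.8 = 3.0 points (sensitivity, AUC 0.92) and 0.67 × 9.3 = 6.2 points (specificity, AUC 0.70).

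Error of the Youden index in a single trial (RMSE, AUC 0.70 / 0.80 / 0.92):

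| Split | Apparent | Leave-one-out | Bootstrap-corrected |
|---|---|---|---|
| 21/16 | 0.198 / 0.180 / 0.151 | 0.208 / 0.182 / 0.148 | 0.145 / 0.142 / 0.129 |
| 30/7 | 0.252 / 0.238 / 0.201 | 0.230 / 0.210 / 0.182 | 0.187 / 0.188 / 0.167 |

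Leave-one-out is nearly unbiased (0.247, 0.416 and 0.644 against true values of 0.257, 0.416 and 0.649 at 21/16), but in a single trial it is less accurate than the bootstrap throughout.

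**The case against.** The best defence concerns weight. The study is described as exploratory (sections 5.1 and 7.1). The ROC step is an addition, and it matches no listed objective or endpoint in sections 6 and 7.7.3. The plan compares markers by correlation and kappa and nowhere schedules a comparison of sensitivity or specificity. All of this stands and limits the point to reporting. It does not remove it: the plan attaches no caveat to this cut-off, although it does label the ST2 cut-off for maintenance of response as exploratory.

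Second, section 8.0 already allows for 95% confidence intervals where applicable. Ordinary Wilson intervals around the uncorrected values covered the true sensitivity and specificity in about 92 to 97% of simulated trials at AUC 0.80 to 0.92. Coverage fell to about 88% for specificity at AUC 0.70 with a 21/16 split. So where ST2 performs as hoped, intervals already convey much of the uncertainty. They still leave the point estimates too high.

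Third, the direction depends on the target. Measured against the best cut-off in the population, a single component can be slightly negative when the spreads differ strongly (sensitivity −1.7 points, specificity −0.8 points), while the sum stays inflated. The claim here is confined to the true accuracy of the cut-off actually selected.

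A reader might infer that the primary result, the AUC or the sample size is compromised. The documents do not support that: the Spearman correlations use no cut-off, the AUC does not depend on one, and the 37 was justified for the correlation alone.

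**Conclusion.** The point holds as a reporting correction of moderate weight. Following section 8.0 as written gives four accuracy figures that are too high on average relative to the true accuracy of the selected cut-off. The size is conditional: about 5 to 9 points per measure under a binormal marker, AUC 0.70 to 0.92, Youden and 21/16, and about 12 to 17 points for specificity at 30/7. The documents give neither the AUC nor the class split for this population, so these are illustrations and not forecasts. It would be too strong to conclude that ST2 is a poor marker or that the published 83%/83% is inflated in the same way; the documents do not say how those figures were obtained.

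**What to change.** Amend section 8.0 as follows.

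1. Name the cut-off criterion, for example Youden.
2. Report the AUC with its 95% CI.
3. Report sensitivity, specificity, PPV and NPV both as apparent and as bootstrap optimism-corrected values, resampling active and inactive subjects separately and reselecting the cut-off in each resample. Give approximate 95% CIs for sensitivity and specificity. Wilson intervals centred on the corrected values covered the truth in 93 to 97% of simulated trials. Bootstrap percentile intervals shifted by the optimism fell as low as 51% for specificity at 30/7 and are best avoided. Interval coverage for PPV and NPV was not checked.
4. State that the correction is partial, that the cut-off was derived and assessed in the same subjects, and that it needs external validation. Do not write a fixed share of bias removed into the SAP, because that share depends on the assumed distribution and split.
5. Apply the same caveat to the week-6 ST2 cut-off for maintenance of response, which rests on a smaller subset, and to the golimumab-level cut-off. Apply the same correction to any accuracy figures reported for them.

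Leave-one-out is an optional check.

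The cost is SAP wording and a few lines of code; no extra subjects or samples are needed. The downside is less favourable figures: at 21/16, sensitivity and specificity fall by about 3 to 6 points. About a third of the bias remains there and up to about half at 30/7, which is why the limitation statement is needed as well.

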Recent data showed that sST2 levels correlate positively with the severity of colonic mucosal disease and inflammatory cytokines (IL-6, IL-33 and TNF) (Beltrán et al., 2010; Pastorelli et al., 2010; Díaz-Jiménez et al., 2011). Diaz-Jimenez and his group demonstrated that sST2 has a good performance for discriminating between active and inactive UC in TNF inhibitors naïve patients, based on clinical, endoscopic and histopathological characteristics: active UC = 235.8 pg/mL (90.65-367.90); inactive UC = 33.19 pg/mL (20-65.32), for a cut-off value of 74.87 pg/mL (sensitivity=83%, specificity=83%; AUC=0.92 [0.86-0.97, p<0.0001]). This study also showed that sST2 serum levels from UC patients significantly correlate to endoscopic Mayo score ( $r=0.76$ ,  $p<0.0001$ ) as well as histopathological score ( $r=0.67$ ,  $p<0.0001$ ) (Díaz-Jiménez et al., 2011).

Treatment with TNF inhibitors modulates circulating IL-33 and sST2 levels. In a small cohort of IBD patients, Pastorelli and his group evaluated Infliximab's acute and long term effects and observed a decrease of IL-33 and an overall decrease in the IL-33/sST2 ratio, with a greater impact in UC patients (Pastorelli et al., 2010).

In a rheumatoid arthritis study, serum levels of IL-33 were shown to decrease significantly in responders to TNF inhibitors vs. non responders, and sustained elevation of serum and/or synovial levels of IL-33 were suggested to have a possible association with poor response to TNF inhibitors (Matsuyama et al., 2012).

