### 7.3.1 Subject Inclusion Criteria

To be eligible for the study, subjects must meet all of the following criteria:

1. Are men or women of any race,  $\geq 18$  and  $\leq 65$  years of age;
2. Had UC diagnosed prior to screening, based on results from a biopsy collected at an endoscopy procedure;
3. Have moderate to severe active UC with total Mayo score of 6 to 12, inclusive at baseline, AND endoscopic Mayo subscore (fibrosigmoidoscopy), greater than or equal to 2;
4. Regarding prior or current medication for UC:

- 4.1 Subjects must have responded inadequately to corticosteroids (at least 40mg) with or without 5-ASA, or subjects must be steroid-dependent (unable to reduce steroids below 10mg within 3 months of starting steroids and/or have relapsed within 3 months of stopping steroids)
- AND
- 4.2 Subjects must have responded inadequately to AZA or 6-MP (must have been receiving it for the last 12 weeks) or are intolerant or have medical contraindications to these agents
5. Subjects must be naïve to TNF inhibitors;
6. Subjects must be eligible to start golimumab treatment according to SmPC;
7. All subjects must either have had a colonoscopy to assess for the presence of adenomatous polyps within 5 years of study inclusion or a colonoscopy to assess for the presence of adenomatous polyps at the screening visit. The adenomatous polyps must be removed prior to the first administration of golimumab;
8. All subjects who have had extensive colitis for  $\geq$  8 years, or disease limited to the left side of the colon for  $\geq$  10 years, must either have had a colonoscopy to assess the presence of dysplasia within 1 year prior study inclusion or a colonoscopy to assess the presence of malignancy at the screening visit;
9. The investigator has discussed with the subject the information contained in the informed consent regarding anti-TNF therapies and the potential risk of cancer, and has reviewed with the subject country-specific guidance (local practice) on cancer screening and the impact of life-style choices (e.g., smoking) on the risk of developing cancer.
10. Have an acceptable Tuberculosis Assessment:

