### **7.7.3.2 Secondary endpoints**

- To correlate serum soluble ST2 levels with endoscopic activity (assessed by endoscopy subscore of Mayo score) at week 16 in moderate to severe UC subjects under golimumab treatment.
- To correlate serum soluble ST2 levels with histological activity (assessed by Geboes index) at week 16 in moderate to severe UC subjects under golimumab treatment.
- To correlate serum soluble ST2 levels with fecal calprotectin levels at week 6 and week 16.
- To correlate serum soluble ST2 levels with clinical activity (assessed by total Mayo score) at week 6 and week 16.

- To evaluate the potential of serum soluble ST2 as a predictor of endoscopic response to golimumab by comparing Mayo endoscopic activity (activity [subscore  $\geq$  2] or no activity [subscore 0 or 1]) with ST2 at baseline and change of ST2 between baseline and Week 6.
- To correlate serum soluble ST2 levels with maintenance of endoscopic response to golimumab by comparing subjects who achieved endoscopic response at week 6 [subscore 0 or 1] and maintained through week 16 versus subjects who did not maintain response throughout the same period, regarding serum soluble ST2 at baseline, week 6 and change between baseline and week 6.
- To correlate Mayo endoscopic score with UCEIS overall score at week 6 and week 16 in moderate to severe UC subjects under golimumab treatment.

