- the correlation between serum soluble ST2 histological activity (measured by Geboes index score) at 16 weeks in UC subjects receiving golimumab, through the Spearman correlation coefficient.
- Correlations will also be performed between serum soluble ST2 levels and endoscopic and histological activity at baseline.
- Serum soluble ST2 levels at baseline, Week 6 and Week 16 will be correlated with fecal calprotectin levels at baseline, week 6 and week 16 through Pearson correlation coefficient or Spearman correlation coefficient in case the normality assumption was not verified. The two biomarkers will be categorized by the cut-offs and Cohen's kappa coefficient will be obtained.

- Serum soluble ST2 levels at baseline, week 6 and week 16 will be correlated with clinical activity (total Mayo score), through Spearman correlation coefficient.
- Comparative analyses of means (active disease versus inactive disease at week 6) with serum ST2 at baseline and change between baseline and week 6.
- Comparative analyses of subjects who achieved response at week 6 and maintained through week 16 versus subjects who did not maintain response, regarding serum soluble ST2 at baseline, week 6 and change between baseline and week 6. ROC curve analysis of the serum soluble ST2 at week 6 regarding maintenance of response between week 6 and 16 will be performed. This exploratory analysis will detect the cut-off levels of the serum soluble ST2 at week 6 associated with maintenance of response.
- It will be investigated the correlation of Mayo endoscopic score at baseline, week 6 and week 16 with UCEIS overall score at baseline, week 6 and week 16, through the Spearman correlation coefficient.

For the exploratory endpoints the following analysis will be performed:

- Serum golimumab levels at week 6 and week 16 will be correlated with clinical activity (total Mayo score) at the same time points, through Spearman correlation coefficient.
- Mean serum golimumab levels will be compared between patients with active disease (total Mayo score  $>2$ ) and patients with inactive disease (total Mayo score  $\leq 2$  points with no individual subscore  $> 1$ ) at week 6 and 16 through T-test for independent groups or Mann-Whitney test according to the assumption validations of the statistical test.

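### The predictor-of-endoscopic-response analysis compares baseline ST2 without regard to entry endoscopic subscore, so a positive result cannot show that ST2 predicts response beyond baseline severity

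*Combined protocol and SAP*

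**What the plan says.** Section 7.7.3.2 sets the endpoint: "To evaluate the potential of serum soluble ST2 as a predictor of endoscopic response to golimumab by comparing Mayo endoscopic activity", where activity is a subscore of 2 or more and no activity is 0 or 1. The ST2 quantities compared are the baseline level and the change from baseline to week 6. Section 8.0 gives the matching analysis: "Comparative analyses of means (active disease versus inactive disease at week 6) with serum ST2 at baseline". It plans the same comparison for the ST2 change over the first six weeks. Its general rule for two independent samples is a t-test or a Mann-Whitney test. Section 8.0 has no regression model, covariate, stratified test or subgroup by entry subscore. The statement in Section 7.4.1.2 that no stratification will be done concerns treatment assignment, not analysis.

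Three other places bear on the point:

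- Section 7.3.1, item 3, requires an "endoscopic Mayo subscore (fibrosigmoidoscopy), greater than or equal to 2". On the 0–3 scale everyone therefore starts at 2 or 3.
- Section 5.1 reports from a prior study that "sST2 serum levels from UC patients significantly correlate to endoscopic Mayo score" (r = 0.76). That study included both active and inactive UC.
- Section 8.0 also plans correlations of ST2 with endoscopic and histological activity at baseline, and bivariate correlations among ST2, calprotectin, CRP and the endoscopic score.

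**The concern.** Because response is an absolute status and not a change, a subject entering at 2 needs a 1-point fall and a subject entering at 3 needs at least 2 points. Entry severity may therefore influence who responds. The trial's premise is that ST2 follows endoscopic severity, so baseline ST2 may carry the same information. If both hold, baseline ST2 will differ between week-6 active and inactive disease even when it says nothing beyond the screening endoscopy.

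What is at stake is the wording of the conclusion. The planned comparison can support a statement that baseline ST2 is associated with week-6 endoscopic status. It cannot support a statement that ST2 predicts response independently of how inflamed the mucosa was at entry, and nothing in Section 8.0 keeps the two apart.

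**Working it through.** **The plan's own figure.** Section 8.0 says "it is expected to include a total of 37 subjects for analysis" and that "there is a probability of 80% that the lower limit of a one-sided 95% confidence interval is higher than 0.50". The second statement is conditional on a correlation of 0.75 or more. Taking 0.75 as the true correlation and using Fisher's z:

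n = ((1.645 + 0.842) / (atanh 0.75 − atanh 0.50))² + 3 = (2.487 / 0.4236)² + 3 = 37.45

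Power at 37 is 79.5%, so the figure reproduces. It covers the primary correlation only; no power is stated for the predictor comparison.

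**Inputs from the documents.** n = 37; entry subscore 2 or 3; inactive = 0 or 1; r = 0.76 (Section 5.1); week-6 mucosal healing 42% in a prior golimumab trial (Section 5.1), or about 0.42 × 37 = 15.5 healed subjects.

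**Assumptions, not in the documents.** The share entering at 3 (30–50%), healing by entry subscore, the ST2 step between subscores 2 and 3, and a two-sided 0.05 level.

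**Where a step of about 1 SD comes from.** Suppose r = 0.76 held linearly over scores 0–3 in equal shares. The SD of the score is √1.25 = 1.118. The step per point is 0.76/1.118 = 0.680, and the residual SD is √(1 − 0.76²) = 0.650. The step is then 0.680/0.650 = 1.05 within-score SD. A bivariate-normal version with three assumed score mixes gives 1.1–1.3 SD. Both extrapolate from a study spanning active and inactive disease.

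**Size of the carried-over difference.** Let ST2 depend only on entry subscore, with step d. Between unhealed and healed subjects:

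- mean difference = d × [P(entry 3 | unhealed) − P(entry 3 | healed)]
- AUC = 0.5 + [Φ(d/√2) − 0.5] × the same bracket

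Take a middle case: half enter at 3, healing is 57% from 2 and 27% from 3, and d = 1.

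- P(3 | unhealed) = 0.365/0.580 = 0.629
- P(3 | healed) = 0.135/0.420 = 0.321
- bracket = 0.308
- mean difference = 0.31 SD
- AUC = 0.5 + 0.260 × 0.308 = 0.58

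Neither formula contains n, so the difference does not shrink in a larger study. In simulation of this case the unadjusted rejection rate is 10% at n = 37, 25% at 100 and 52% at 200.

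**Rejection rates at n = 37.** Unadjusted Mann-Whitney, no ST2 effect given entry subscore, overall healing held at 42%, 1,500 runs per cell. Each cell shows 30% / 50% entering at 3.

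| Healing gap, entry 2 minus entry 3 | no step | 0.5 SD | 1.0 SD | 1.5 SD |
|---|---|---|---|---|
| 20 points | 4.1 / 4.3% | 5.3 / 5.3% | 7.3 / 7.7% | 9.0 / 10.3% |
| 30 points | 4.5 / 4.3% | 6.8 / 7.3% | 9.9 / 11.7% | 13.4 / 18.6% |
| 40 points | 5.6 / 4.7% | 7.9 / 9.1% | 13.3 / 18.8% | 21.9 / 31.1% |
| 50 points | 3.9 / 4.7% | 9.5 / 10.3% | 20.5 / 27.4% | 33.3 / 46.7% |

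With no healing gap and a 1.0 SD step the rates are 5.6 / 5.1%. A van Elteren test stratified by entry subscore rejects in 3.4–6.0% across all cells. The simulation standard error near 5% is √(0.05 × 0.95/1500) = 0.6 points.

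A second set used 6,000 runs, the 1.05 SD step and overall healing of 40–52%. The unadjusted test rejects in 7–9% (healing 50% v 30%), 9–13% (55% v 25%) and 17–23% (65% v 20%); the stratified test rejects in 4.4–4.9%. With a 0.5 SD step the unadjusted rate is about 6–9%, and with no step about 5%.

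**Cost of stratifying.** Now let healing depend on ST2 alone (assumed log-odds 0.8 or 1.2 per within-score SD), with overall healing of 42%. Unadjusted power is 63–65% and 90%; van Elteren power is 51–52% and 79–81%. The loss is about 9–14 points.

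These calculations cover baseline ST2 only, not the change to week 6.

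**The case against.** The strongest reply is that the protocol does not ask whether ST2 adds to endoscopy. It asks about the potential of ST2 as a predictor, and Section 5.1 wants a simple non-invasive marker in a setting where surrogates might replace endoscopy. For that purpose, a serum marker that forecasts healing because it reflects mucosal severity is a useful finding. This stands, and it is why the unadjusted comparison should stay.

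A reader might infer from the 7–23% that the planned test has an inflated type I error. It does not. In those scenarios ST2 truly has a marginal association with healing, so the test's own null is false. The figures are false-positive rates only for the separate question of value beyond endoscopy.

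A reader might also take r = 0.76 as evidence that ST2 differs between subscores 2 and 3. It is not. The same study found 235.8 pg/mL in active and 33.19 pg/mL in inactive UC, so much of the correlation could come from that contrast, and this trial enrols only 2 and 3. The documents give neither ST2 nor healing by entry subscore; if either is flat, the rate is about 5%.

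The plan has some mitigation. The study is declared exploratory, the endpoint is secondary, no decision rule hangs on it, and the planned baseline and bivariate correlations would reveal a link between ST2 and severity. They would not show whether ST2 predicts response within an entry subscore.

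**Conclusion.** The point holds as a limit on interpretation. The planned comparison cannot distinguish ST2 predicting response from ST2 standing in for entry severity. At n = 37, with no added effect of ST2, the unadjusted test is positive in about 5% of trials if ST2 does not differ between subscores 2 and 3, 6–9% at a 0.5 SD step, and 7–23% at about 1 SD with healing gaps of 20–45 points, against about 5% when stratified. The upper end needs both the 1 SD step and a 45-point gap, and both are assumptions.

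A reader might go further and conclude that the unadjusted analysis is invalid, or that a stratified test should take its place. The documents do not support either. The marginal question is a legitimate reading of the objective, and replacement would cost power in the case where ST2 is the true driver.

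**What to change.** In Section 8.0, for the predictor endpoint:

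1. Keep the unadjusted comparison of baseline ST2 between week-6 active and inactive disease.
2. Add the same comparison stratified by screening endoscopic subscore (2 v 3), using a van Elteren test. A Firth logistic model of week-6 inactive disease on baseline ST2 and entry subscore would also serve; the penalty is advisable with about 15–16 healed subjects expected.
3. Show baseline ST2 by week-6 status separately within entry subscores 2 and 3.
4. State that any claim that ST2 predicts response independently of baseline endoscopic severity rests on the stratified result, and that the unadjusted result alone supports only a marginal association.

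The cost is SAP wording, one extra test and one display. The screening subscore is already collected on every subject, so no new data are needed. The stratified test has lower power than the planned one, by the 9–14 points shown above, so a non-significant stratified result at this size should not be read as evidence that ST2 adds nothing.
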